9.1 DESCRIPTION OF ANALYSIS SETS

9.1.1 SAFETY ANALYSIS SET

Subjects who have received at least one dose of Durvalumab + AVB-S6-500 combination treatment will be included in the Safety Analysis Set. Safety will be monitored in the monotherapy phase and in the combination therapy phase.

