2. STUDY OBJECTIVES

2.1 PRIMARY

To determine toxicity profile of the combination of AVB-S6-500 and durvalumab therapy

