The IV line will be flushed with a volume of IV diluent equal to the priming volume of the infusion set used after the contents of the IV bag are fully administered or complete the infusion according to institutional policy to ensure the full dose is administered.

During combination treatment, durvalumab will be administered prior to AVB-S6-500. IV line flushing in between IP treatments will be performed per institutional policy.

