6.2 DEFINITION OF DOSE-LIMITING TOXICITIES

DLTs will be evaluated during the safety lead-in (dose de-escalation phase) of the trial. The period for evaluating DLTs will be from the time of first administration of study drug until 6 weeks (1.5 cycles). Any treatment-related toxicities that first occurred during the DLT period must be followed for resolution to determine if the event qualifies as a DLT as specified in the DLT criteria below. Patients who do not remain on the study up to this time for reasons other than DLT will be replaced with another patient at the same dose level. Grading of DLTs will follow the guidelines provided in the Common Terminology Criteria for Adverse Events (CTCAE) version 5.0.

To be considered a DLT, an AE must be at least possibly related to the investigational product or regimen and meet the criteria listed below. Toxicity that is clearly and directly related to the primary disease or to another etiology is excluded from this definition. The DLT criteria are specified in the following lists.

Hematologic toxicity:

- Grade ≥ 3 neutropenia complicated by fever $>38.3^{\circ}\text{C}$
- Grade ≥ 3 neutropenia that does not improve \leq Grade 1 within 7 days
- Grade 4 neutropenia (lasting more than 7 days)
- Grade ≥ 3 thrombocytopenia with significant bleeding
- Grade 3 thrombocytopenia that is not associated with clinically significant bleeding and does not improve by at least 1 grade within 7 days
- Grade 4 thrombocytopenia (regardless of duration)
- Grade 4 anemia (regardless of duration)

Non-hematologic toxicity:

- Any Grade 4 non-immune-mediated AE
- Any Grade 4 immune-mediated AE, excluding endocrinopathies
- Any Grade 3 non-immune mediated AE, including fatigue, that does not resolve to \leq Grade 1 or baseline within 30 days with optimal medical management
- Any Grade 3 immune-mediated AE – excluding diarrhea/colitis, pneumonitis, hepatitis, rash, neurotoxicity, myocarditis, myositis/polymyositis, endocrinopathies and nephritis – that does not resolve to \leq Grade 2 or baseline within 15 days and to \leq Grade 1 within 30 days after onset of the event, despite optimal medical management including systemic corticosteroids

- Grade 3 diarrhea or colitis
- Grade 3 noninfectious pneumonitis
- Grade 2 noninfectious pneumonitis that does not resolve to \leq Grade 1 within 3 days of the initiation of maximal supportive care

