The trial will be completed after the RP2D is determined as described above. The section below is maintained in the protocol in order to reference the original design and will no longer apply.

After the RP2D is determined, subsequent patients will be randomized in a 3:1 manner for enrollment into the respective AVB-S6-500 and Durvalumab monotherapy arms. We estimate accrual rate of 3 patients per month. We anticipate a dropout rate of approximately 8-10% due to possible toxicity as seen in prior literature of checkpoint inhibitor therapy [61], [62], and subsequent inability to proceed to combination treatment. All patients who complete the monotherapy treatment phase will proceed to combination treatment, at which time receipt of at least one dose of combination therapy at the final determined dosing defines evaluable patients. As mentioned above, should the safety lead-in phase in the combination treatment require dose adjustment, only those patients who received the RP2D and completed one cycle of combination treatment will be considered evaluable for the primary outcome of response rate to combination therapy and used for making go/no-go decision as described below.

In terms of outcome assessment of response rate and toxicity to combination therapy, the Bayesian optimal phase 2 (BOP2) design is utilized to jointly monitor toxicity and efficacy [63]. The first 12 patients to receive combination treatment constitutes the first stage. Of these N=12 patients, if 1 or more responses are detected and no more than 5 DLTs are observed, the trial will proceed to the second-stage and enroll an additional 15 patients. Of note, more than 3 responses and fewer than 10 DLTs in the total study cohort will indicate statistically significant improvement in response and toxicity.

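### The only Safety Analysis Set requires a combination dose, so a lead-in patient stopped by toxicity after durvalumab alone could count as a DLT yet fall outside the safety results

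*Combined protocol and SAP*

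**What the plan says.** - **Objective.** Section 2.1 has a single primary objective: "To determine toxicity profile of the combination of AVB-S6-500 and durvalumab therapy".
- **Safety set.** Section 9.1.1 states: "Subjects who have received at least one dose of Durvalumab + AVB-S6-500 combination treatment will be included in the Safety Analysis Set". It adds: "Safety will be monitored in the monotherapy phase and in the combination therapy phase". No other safety population is defined.
- **Safety analyses.** Sections 9.2 and 9.2.1 call for adverse event tables, the proportion discontinuing for adverse events and an unacceptable-toxicity rate, with 90% confidence intervals for the two proportions. Neither section names the population.
- **Order of infusion.** Section 5.1.2: "During combination treatment, durvalumab will be administered prior to AVB-S6-500". Section 5.2.2 repeats this.
- **Dose finding.** Section 6.2: "The period for evaluating DLTs will be from the time of first administration of study drug until 6 weeks". On replacement: "Patients who do not remain on the study up to this time for reasons other than DLT will be replaced". The footnote to Table 12 in Section 9 divides the number with a DLT by all patients treated at the current dose.
- **Status.** Section 3.1 records that enrollment ended after the fifth evaluable lead-in subject. A notice in Section 9, placed before the Phase II text, says the material below it is kept for reference and has ceased to apply.

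**The concern.** Dose finding and the safety summary use different entry rules. Dose finding takes in a patient at her first exposure to either drug. The safety set takes her in only once she has had a dose of the combination. Because durvalumab goes first, there is an interval in which a treated patient belongs to the first population but not the second.

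A patient who leaves in that interval because of toxicity takes both her event and herself out of the safety summary. The exclusion is then caused by the outcome being measured, and it lowers the observed rate. Toxicity is the only primary objective and the lead-in is very small, so one such patient would be visible in the results. The DLT count and the safety tables could also disagree about the same dose level.

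**Working it through.** **1. Can a treated patient be outside the set?** Both drugs are scheduled for Day 1 of Cycle 1 (Table 6), durvalumab first, with a standard infusion time of one hour. Section 4.3.1 lists an infusion reaction of Grade 3 or higher among the reasons to give no further product, and the infusion-reaction table in Appendix A agrees. Section 5.1.3 also stops drug at that grade but allows one Grade 3 reaction that resolves within 6 hours without prophylaxis. These passages must be reconciled. On any of them some reactions end treatment, and a patient stopped during durvalumab has had no combination dose. Section 9.1.1 is also silent on whether a partly delivered first AVB-S6-500 infusion counts.

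**2. Can she be a DLT?** Section 6.2 excludes a first Grade 3 infusion reaction without steroid prophylaxis that resolves within 6 hours. It includes any Grade 4 non-immune-mediated event, and Grade 3 events of that kind that do not resolve to Grade 1 or baseline within 30 days. So a Grade 4 or persistent Grade 3 reaction qualifies. She is not replaced, and she stays in the Table 12 denominator.

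**3. What if she is stopped but is not a DLT?** She has then left for a reason other than DLT, so she is replaced in dose finding and is also outside the safety set. Yet Section 11.1 counts a treatment-related event of Grade 3 or more, or discontinuation for side effects, as unacceptable toxicity.

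**4. The plan's own toxicity precision.** Section 9 gives a 90% half-width of 0.127 for an expected 0.20 with N = 27. Check: 1.645 × √(0.20 × 0.80 / 27) = 0.1266, which reproduces. It belongs to the Phase II text that has ceased to apply. The plan states no precision for the lead-in.

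**5. Effect of one omission.** If x of n treated patients have the event and one of those x is left out, the rate falls from x/n to (x − 1)/(n − 1). The drop is (n − x) / [n(n − 1)], which is never negative. Exact (Clopper-Pearson) 90% limits are the 5% quantile of Beta(x, n − x + 1) and the 95% quantile of Beta(x + 1, n − x). The counts below are assumed.

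| All treated | 90% CI | Under 9.1.1 | 90% CI | Drop |
|---|---|---|---|---|
| 1/3 = 33% | 2-87% | 0/2 = 0% | 0-78% | 33 points |
| 1/6 = 17% | 1-58% | 0/5 = 0% | 0-45% | 17 points |
| 2/6 = 33% | 6-73% | 1/5 = 20% | 1-66% | 13 points |

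For n = 6 and x = 1: (6 − 1) / (6 × 5) = 0.167. In the first row, one DLT in three blocks escalation under Table 12 (which de-escalates at 1 of 3) and under the thresholds in the Section 9 text (0.333 lies between 0.236 and 0.359, so stay). Those two rules differ on this count, which is a separate matter to reconcile. The safety set would show no event.

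**The case against.** The strongest reply is that the route is narrow, and that stands. The patient must be stopped in the interval around one durvalumab infusion. Delayed immune-mediated events, which fill much of the DLT list, arise in patients already inside the set, and many first Grade 3 infusion reactions are not DLTs. No document reports such a patient.

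It is also fair that Sections 9.2 and 9.2.1 name no population, so the omission from the tables is inferred from this being the only safety set defined. The event itself would not be lost as data: Section 8.3.1 collects adverse events from the first protocol-specific procedure, and Section 8.1.3.1 makes infusion reactions events of special interest. Dose selection is unaffected, because it uses all patients treated at the dose.

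A set limited to combination-treated patients arguably matches an objective about the combination. That holds for a description of what follows both drugs. It does not settle how to count a patient assigned to the combination whom toxicity prevented from completing the first dose.

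A reader might infer a larger problem from the Phase II text, which says: "We anticipate a dropout rate of approximately 8-10% due to possible toxicity", and conclude that all those patients would be lost from the safety results. The documents do not support carrying that forward. Section 9 says the design has ceased to apply, Section 3.1 says enrollment ended in the lead-in, and monotherapy patients were never part of dose finding. Sections 9.1.1, 9.2.2 and 11.1 also provided for looking at safety in the monotherapy phase.

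**Conclusion.** The concern holds for the lead-in, on the literal text. The set definition and the DLT rules admit different patients, and the difference can be caused by toxicity. Its possible size is one patient in a group of about five or six: for example 17% against 0%, with wide, overlapping intervals. That rests on assumed counts, on Section 9.1.1 being the population meant for 9.2 and 9.2.1, and on the patient being summarised under her assigned dose level.

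A reader might go further and conclude that the reported toxicity is biased. The documents do not show that. If no patient stopped after durvalumab alone, correcting the definition changes no number.

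The scope of the Section 9 notice adds an ambiguity. If it reaches 9.1, the lead-in has no defined safety set at all. Section 9.1 needs a correction on either reading.

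**What to change.** 1. In 9.1.1, define the Safety Analysis Set as all subjects who received any amount of durvalumab or AVB-S6-500.
2. Summarise it primarily by assigned dose level, with combination-treated subjects as a labelled subset. One primary basis has to be chosen: splitting by drug actually received would put the durvalumab-only patient in a separate row and leave the combination rate at 0/5 in the illustration.
3. Name this set in 9.2 and 9.2.1 for the adverse event tables, the discontinuation rate and the unacceptable-toxicity rate.
4. State that 9.1 applies to the lead-in despite the notice in Section 9.
5. Leave the efficacy set in 9.1.2 unchanged.

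The cost is a few sentences. Sample size, data collection and treatment rules do not change. The one downside is that reported toxicity may be slightly less favourable.

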9.1.2 EFFICACY ANALYSIS SET

Subjects who have received at least one dose of Durvalumab + AVB-S6-500 combination treatment will be included in the Efficacy Analysis Set. Efficacy will be monitored in the combination therapy phase.

9.2 METHODS OF STATISTICAL ANALYSES

We will use descriptive statistics to summarize the demographic and clinical characteristics of the subjects. We will estimate the objective response rate (ORR) along with a 90% confidence interval. Response is defined in **Section 7.2**. We will estimate the median immune-related progression free survival (irPFS) after treatment with combination durvalumab and AVB-S6-500 using the product-limit estimator of Kaplan and Meier. When appropriate, we will model irPFS using Cox proportional hazards regression as an exploratory analysis because of the small sample size. Immune-related PFS is defined as the time from the date of dual therapy treatment initiation to the date of initial radiologic evidence of progressive disease (**Section 7.2**) or death. Those who are immune-related progression-free and alive will have irPFS censored at their last clinic visit.

Molecular and immunological changes will be summarized with standard descriptive statistics. Changes in T cell populations and proliferation will be calculated along with 95% confidence intervals and compared between pre and posttreatment biopsies using two sample t-test. Similar summaries will be used to compare proportions of macrophage phenotypes. We will tabulate adverse events by grade, and by relationship to study drug. We will estimate the proportion of subjects that discontinue treatment due to adverse events with 90% confidence intervals. We will estimate the unacceptable toxicity rate with a 90% confidence interval.

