2.2 SECONDARY

1. To estimate objective response rate to combination AVB-S6-500 and durvalumab therapy
2. To estimate the median immune-related progression free survival (irPFS) as well as overall survival OS by RECIST 1.1 after treatment with combination durvalumab and AVB-S6-500
3. To investigate molecular and immunological changes associated with the combination of AVB-S6-500 and durvalumab; specifically to describe changes in T cell populations (including but not limited to CD3, CD8, CD4, FOXP3) and cell proliferation, as well as report changes in the proportion of macrophage phenotypes M1 and M2 (with phenotypic markers potentially including arginase1, CD11b, PDL-1, and CD206)

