3. ORIGINAL STUDY DESIGN

This is a randomized phase I/II trial of the combination of immune checkpoint inhibitor therapy and AXL inhibition in patients with recurrent platinum resistant EOC. The design is based on the clinical rationale that the combination of durvalumab and AVB-S6-500 may have increased efficacy but at the risk of potentially greater toxicity. This trial will determine appropriate combination dosing and then, based on efficacy and safety assessments, allow for development of a superior suitable regimen for a follow-up phase III investigation based on these efficacy and toxicity tradeoffs. It will also be informative regarding response rates associated with this combination regimen and will generate key preliminary data to determine impact on irPFS and if pretreatment with either durvalumab or AVB-S6-500 impacts subsequent response to the combination of both therapies. Furthermore, translational correlative studies will include immune profiling and ribonucleic acid (RNA) expression analysis of tumor at enrollment, following monotherapy, and on combination treatment to investigate biological correlates for response, possible sensitization of immune microenvironment, and any indication of adverse event. Progression during investigational agent treatment cycles will be defined based on immune-related response criteria (irRC; including computed tomography (CT) confirmation at least 5 weeks apart to determine progression).

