7. DISEASE EVALUATION AND METHODS

7.1 MODIFIED RECIST V1.1

The response to immunotherapy may differ from the typical responses observed with cytotoxic chemotherapy. These difference include the following [59], [60]:

- Response to immunotherapy may be delayed,
- Response to immunotherapy may occur after PD by conventional criteria,
- The appearance of new lesions may not represent PD with immunotherapy, and
- SD while on immunotherapy may be durable and represent clinical benefit.

Based on the above-described unique response to immunotherapy and based on guidelines from regulatory agencies, e.g., European Medicines Agency's "Guideline on the evaluation of anticancer medicinal products in man" (EMA/CHMP/205/95/Rev.4) for immune modulating anticancer compounds, we will implement the following modifications in addition to standard RECIST 1.1 criteria.

- RECIST will be modified so that PD must be confirmed at the next scheduled visit, preferably, and no earlier than 5 weeks after the initial assessment of PD in the absence of clinically significant deterioration. Treatment with durvalumab and AVB-S6-500 would continue between the initial assessment of progression and confirmation for progression.
- In addition, patients may continue to receive durvalumab and AVB-S6-500 beyond confirmed PD in the absence of clinically significant deterioration and if investigators consider that patients continue to receive benefit from treatment.

Modification of RECIST as described may discourage the early discontinuation of durvalumab and AVB-S6-500 and provide a more complete evaluation of its antitumor activity than would be seen with conventional response criteria. Nonetheless, the efficacy analysis will be conducted by programmatically deriving each efficacy endpoint based on RECIST 1.1 criteria.

Of note, clinically significant deterioration is considered to be a rapid tumor progression that necessitates treatment with anticancer therapy other than durvalumab or with symptomatic progression that requires urgent medical intervention (e.g., central nervous system metastasis, respiratory failure due to tumor compression, spinal cord compression).

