7.2.4 EVALUATION OF OVERALL RESPONSE WITH MODIFICATIONS

Confirmation of CR, PR, as well as PD is required by a repeat, consecutive assessment no less than 5 weeks from the date of first documentation. Treatment with study regimen will continue between the initial assessment of PD and confirmation for PD. If PD is confirmed by the second confirmatory scan, the associated time of progression will be reported as that of the initial imaging study revealing progression. In the absence of clinical deterioration, such modifications to the RECIST criteria may discourage the early discontinuation of the study regimens and provide a more complete evaluation of its antitumor activity than would be seen with conventional response criteria.

Table 10 provides overall responses for all possible combinations of tumor responses in target and non-target lesions with or without the appearance of new lesions.

Table 10. Overall Responses for All Possible Combinations of Tumor Responses

Target Lesions	Non-target Lesions	New Lesions	Overall Response
Complete response	Complete response (or no non-target lesion)	No	Complete response
Complete response	Not evaluable ^a	No	Partial response
Complete response	Non-complete response/non-progressive	No	Partial response
Partial response	Non-progressive and non-evaluable ^a	No	Partial response
Stable disease	Non-progressive and non-evaluable ^a	No	Stable disease
Not all evaluated	Non-progressive	No	Not evaluable
Progressive disease	Any	Yes/No	Progressive disease ^b
Any	Progressive disease	Yes/No	Progressive disease ^b
Any	Any	Yes	Progressive disease ^b

^a Not evaluable is defined as either when no or only a subset of lesion measurements are made at an assessment

^b Disease progression requires confirmatory radiologic assessment

Confirmation of progression guidelines are set for the following reasons:

- for patient management and treatment decisions and
- in the absence of significant clinical deterioration, to promote the collection of additional scans after the first radiologic RECIST 1.1 assessment of progressive disease (PD) in order to distinguish pseudoprogression from true radiologic progression, also known as RECIST 1.1 modified for confirmation of progression.

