Confirmed objective disease progression refers to either of the following scenarios: 1. clinical progression/deterioration followed by a radiologic verification scan (PD by RECIST 1.1); or 2. in the absence of significant clinical deterioration, radiologic PD by RECIST 1.1 followed by a second radiologic confirmation scan with PD assessed according to the specific confirmation of progression criteria listed below. RECIST 1.1 modified for confirmation of progression refers to the second scenario above. The confirmatory scan should occur preferably at the next scheduled imaging visit and no earlier than 5 weeks following the date of the immediate prior assessment of RECIST 1.1 PD.

Immediate prior radiologic progression would be considered confirmed if any the following criteria are met in the confirmatory scan:

- $\geq 20\%$ increase in the sum diameters of target lesions (TLs) compared with the nadir at 2 consecutive visits, with an absolute increase of at least 5 mm in sum of diameters compared to nadir,
- and/or significant progression (worsening) of non-target lesions (NTLs) and/or of pre-existing new lesions at the confirmatory scan time-point compared with the immediate prior time-point (Note: Pre-existing new lesions are evaluated as NTLs at the confirmatory scan time-point), and/or
- additional new unequivocal lesions at the confirmatory scan time-point.

To have confirmed objective disease progression, there should be two consecutive assessments meeting the PD definition: the first PD by RECIST 1.1 and the second PD using the confirmation of progression criteria (above). If the first assessment fulfilling the PD definition by RECIST 1.1 is not confirmed, continue with assessments until the next PD by RECIST 1.1, which in turn will need its own immediate subsequent confirmation scan. In the absence of significant clinical deterioration, treatment with study drug may continue between the initial assessment of progression and the scan to confirm progression.

If the confirmation scan confirms progression, then the date of the prior scan with PD should be declared as the date of progression.

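### irPFS is censored at the last clinic visit although progression is established by scan, and the plan does not settle whether a first PD with no later scan is an event in a living patient

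*Combined protocol and SAP*

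**What the plan says.** Section 9.2 runs irPFS from the start of dual therapy "to the date of initial radiologic evidence of progressive disease", with a pointer to Section 7.2, or to death. The censoring rule follows: "Those who are immune-related progression-free and alive will have irPFS censored at their last clinic visit". Section 2.2 lists the secondary objective as "To estimate the median immune-related progression free survival (irPFS) as well as overall survival OS by RECIST 1.1 after treatment".

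Section 7.1 describes a RECIST modified to require confirmation of progression, then adds: "Nonetheless, the efficacy analysis will be conducted by programmatically deriving each efficacy endpoint based on RECIST 1.1 criteria".

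Other sections require confirmation:
- Section 3 defines progression by irRC, "including computed tomography (CT) confirmation at least 5 weeks apart to determine progression".
- Section 7.2.4 opens with "Confirmation of CR, PR, as well as PD is required by a repeat, consecutive assessment no less than 5 weeks".
- Table 10, footnote b, reads "Disease progression requires confirmatory radiologic assessment".
- Section 7.2.4 later states "To have confirmed objective disease progression, there should be two consecutive assessments meeting the PD definition".
- Section 9.2.3 repeats the need for a confirmatory scan.

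Section 7.2.4 also dates a confirmed progression to the first scan, accepts a single verification scan after clinical deterioration, and has the investigator reverse a first PD that the next scan does not confirm.

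On timing, Table 6 in Section 6.5 has visits on Day 1 and Day 15 of each 4-week cycle and imaging every 8 weeks (±7 days). After treatment stops without confirmed progression, visits are every 6 weeks and imaging every 12. The end-of-treatment disease assessment may be skipped if one was done in the preceding 35 days.

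**The concern.** There are two separate problems.

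First, progression cannot be recorded without a scan, but the censoring date is a visit date. A patient last scanned at week 8 and last seen at week 14 stays in the risk set as progression-free for six weeks in which nobody looked.

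Second, an analyst who relies on Sections 2.2, 7.1 and the event wording of 9.2 will count a first PD. One who relies on Sections 3 and 7.2.4 will count it only when confirmed. They agree if the next scan exists, but not if the patient is alive and is never scanned again. Such patients can arise: under Section 4.3.2, withdrawal of consent ends study observation apart from survival follow-up, and the Table 6 footnote on follow-up after treatment ends for progression mentions visits but no imaging.

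At stake is the reported median irPFS. It is estimated only, and no stopping or go/no-go rule uses it.

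**Working it through.** The plan states no irPFS figure, event count or precision, so there is nothing of its own to reproduce. The check covers the direction and size of each problem. The documents give no rates for loss to follow-up, missed scans or progressions without a later scan; all such rates below are assumptions.

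**1. Gap between visit and scan.** With scans every 8 weeks and visits every 2, routine visits fall 2, 4 and 6 weeks after a scan, so the gap reaches 6 weeks. With 12- and 6-weekly schedules off treatment it is again 6 weeks. It is longer if a scan is missed.

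**2. Direction.** The Kaplan-Meier estimate is S(t) = ∏(1 − d_j/n_j). With the same events, a later censoring date never reduces any n_j, so no factor falls. Last-visit censoring therefore gives a curve equal to or above that from last-scan censoring.

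**3. Size of the censoring effect.** Simulation with 400,000 patients per setting: exponential progression with median 13 weeks (from the approximately 3-month median PFS in Section 1.6.1), scans every 8 weeks ±1, visits every 2 weeks, pre-progression death hazard 0.002 per week, post-progression survival median 35 weeks, follow-up to week 52. Both rules use the same events; only the censoring date differs. Week-27 irPFS:

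| Lost per week / scans missed | Deaths after loss | Last scan | Last visit | Full follow-up |
|---|---|---|---|---|
| 0% / 0% | – | 0.262 | 0.262 | 0.262 |
| 1% / 0% | captured | 0.274 | 0.280 | 0.263 |
| 1% / 10% | captured | 0.286 | 0.294 | 0.278 |
| 2% / 20% | captured | 0.310 | 0.328 | 0.295 |
| 1% / 0% | missed | 0.250 | 0.260 | – |
| 1% / 10% | missed | 0.261 | 0.275 | – |
| 2% / 20% | missed | 0.258 | 0.291 | – |

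If progression were dated when it truly occurs, the value would be exp(−27 × ln 2/13) × exp(−0.002 × 27) = 0.237 × 0.947 = 0.225. Full follow-up lies above this because scans detect progression late. On the median, the two rules differ by about 0.1 week at 1%/10% and 0.2 to 0.3 week at 2%/20%. With scans at exact 8-week dates and patients leaving before their next scan, the median was 16 weeks under both rules.

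**4. Texts on a first PD with no later scan, patient alive.**

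| Section | Reading |
|---|---|
| 2.2; 7.1 (closing statement on efficacy derivation) | Event |
| 9.2, event wording | Suggests event, but refers to 7.2 |
| 3; 7.2.4 opening; Table 10 footnote b; 9.2.3 | Confirmation needed |
| 7.2.4, two-assessment rule | Not confirmed, unless one scan followed clinical deterioration |
| 7.2.4, reversal rule | Applies only if a next scan exists |

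Because Section 7.2.4 dates a confirmed PD to the first scan, the word for first evidence in Section 9.2 can be read as a dating rule only. No text closes the gap.

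**5. Size of the event-definition effect.** At 1%/10% with deaths captured, censoring such a PD at its own scan raises week-27 irPFS as follows. It raises the median by 0.1 to 0.3 week.

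| Share of PDs with no later scan | Their survival median 6 weeks | Their survival median 35 weeks |
|---|---|---|
| 5% | +0.5 points | +1.7 points |
| 10% | +1.0 points | +3.4 points |

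*Five patients.* Take first PDs at weeks 8, 8, 16, 24 and 32.
- All counted: S(8) = 3/5 = 0.60 and S(16) = 0.60 × 2/3 = 0.40, so the median is 16 weeks.
- One week-8 PD censored: S(8) = 4/5 = 0.80, S(16) = 0.80 × 2/3 = 0.53 and S(24) = 0.53 × 1/2 = 0.27, so the median is 24 weeks.

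In 40,000 simulated five-patient trials (progression median 13 weeks, exact 8-weekly scans to week 48, no deaths or loss), changing one randomly chosen PD from event to censored altered the median in 39.8%. The change was usually 8 weeks (5th to 95th percentile 8 to 24), and the median was not reached in 4%.

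This is conditional on one such patient. At a 5% or 10% share, the chance of at least one in five is 1 − 0.95⁵ = 0.226 or 1 − 0.90⁵ = 0.410. Multiplying by 0.40 gives about 9% or 16%; simulation that allows more than one gives about 9% to 17%.

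**The case against.** On the censoring date, it can be said that the rule is explicit and reproducible, the effect on the median is about 0.1 week, and the alternative is not always closer to the truth. Against full follow-up, with deaths after loss captured, last-scan censoring errs by +0.8 and +1.5 points (1%/10% and 2%/20%) and last-visit by +1.6 and +3.3. If those deaths are missed, and the same benchmarks (0.278 and 0.295) are used, last-scan errs by −1.7 and −3.7 points and last-visit by −0.3 and −0.4. Deaths can be missed, since Section 4.3 allows for loss to follow-up and for withdrawal from survival follow-up. The small size stands. The reversal holds only against a benchmark that itself runs above true progression-free survival. Against 0.225, last-scan censoring is nearer in every setting with loss.

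On the event definition, the text leans towards counting the first PD: Section 9.2 is the operative definition, Section 7.1 overrides confirmation for efficacy derivation, and Section 7.2.4 gives patient management and scan collection as the purposes of confirmation. Section 3 is headed as the original design, and Section 9.2.3 belongs to an interim look that will not take place. These points have weight. But the opening of Section 7.2.4 and Table 10 still require confirmation, Section 9.2 refers to Section 7.2, and no sentence covers a missing confirmatory scan.

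It is also fair that the 40% is conditional, and that with five uncensored patients the interval from smallest to largest time (weeks 8 to 32 in the example) has coverage of only 1 − 2 × (1/2)⁵ = 93.75%, so an 8-week shift lies well inside it. That limits importance but does not remove the ambiguity. Section 9 says retained phase II text no longer applies without stating how far that extends; Section 2.2 still lists median irPFS, and Section 9.2 holds its only analysis definition.

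**Conclusion.** The concern holds on both points, at low priority and with moderate confidence.

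Last-visit censoring can only leave the curve unchanged or raise it relative to last-scan censoring. The difference is nil if scans are kept and nobody is lost. At 1%/10% it is about 1 point on week-27 irPFS (0.8 with deaths after loss captured, 1.4 if missed). At 2%/20% it is 1.8 or 3.3 points.

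The unsettled status of a first PD with no later scan is the more consequential point, because two analysts following the text could report different medians from the same data. The effect is nil if every first PD is followed by another scan. With five patients, one such case can move the median by a full 8-week scan interval.

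These sizes rest on assumed exponential progression with a 13-week median and on the assumed loss, missed-scan and no-later-scan rates. The conflict between sections, and the direction of the censoring effect, do not.

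**What to change.** In Section 9.2:
- Censor patients who are alive without a counted progression at their last evaluable tumour assessment, or at Day 1 of combination therapy if there is none.
- Count a first RECIST 1.1 PD as an event on its scan date unless a later scan fails to confirm it. A PD with no further scan is then an event.

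Align the analysis definition of progression in Sections 2.2, 3, 7.1, 7.2.4 and 9.2.3 with that rule, and leave the rules on continuing treatment as they are.

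The cost is a few sentences and a few derivation lines, using scan dates already collected. Visits, scans and treatment do not change. Reported irPFS may be slightly shorter.
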